10. STATISTICAL METHODS

10.1 Hypothesis

In this exploratory pilot study a hypothesis testing is non-applicable. We expect that glycaemic control is ameliorated in obese, non-diabetic (but insulin resistant) patients compared to baseline, which might be explained through favourable alterations in gut microbiota composition. Should we be able to find an effect, this pilot trial might serve as a basis for further studies including more patients

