10.2 Determination of Sample Size

In each group we will examine 20 volunteers. This is a pilot trial and findings will serve to plan larger studies in the future. At this moment no power analysis is possible and group size is chosen on the basis of practical considerations rather than statistical estimation. However, according to our experience, a sample size of min. 20 subjects in each arm will most likely allow us to detect large differences in parameters (> 50%) between the treatments groups.

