10.4 Planned Analyses

10.4.1 Datasets to be analysed, analysis populations

In this pilot trial which is purely observational, an analysis per protocol is planned. Drop-outs will be replaced, but baseline data of drop-outs might be included to characterize the baseline population. Baseline values of all three groups will be compared, to rule out any baseline differences. The control group will also be examined twice, and the two time-points should yield similar results. Data from each participant before and after treatment will be analyzed in the sweetener groups. In that way, each participant will serve as his or her own control. Post-treatment values of both treatment groups will then be compared to the control group (without treatment).

In case both sweeteners should have an effect on our endpoints, we might combine the two arms for an additional analysis comparing "no sweetener" (n= 20) vs. "sweetener" (n= 40).

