10.4.2 Primary Analysis

Descriptive statistics will be used for demographic variables, such as age, weight, height and BMI. Hormone and glucose profiles will be analyzed by calculating the area under the concentration-time curve (AUC) from baseline values. The parameters will be tested for normality by the Shapiro-Wilk test method. One-way ANOVA will be applied to describe differences between the groups. Student's paired t-test will be used to test for significant differences between subjects before and after sweetener intake. All statistical analysis will be done using the statistical software package, SPSS for Windows, Version 22.0 (SPSS Inc., Chicago, USA). Values will be reported as mean \pm SEM. Differences will be considered to be significant when P < 0.05. Statistics will be done by the principal investigator with support of Prof. [name], biostatistician.

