10.4.3 Secondary Analyses

No secondary analyses or subgroup analysis is planned.

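### Pooling of the two sweetener arms depends on an undefined effect seen first in the same data, so the pooled estimate is selectively reported and tends to be too large

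*Protocol*

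**What the plan says.** Section 10.2 fixes the arm size: "In each group we will examine 20 volunteers". Section 10.4.1 sets the follow-up values of each sweetener arm against those of the control arm and then adds: "In case both sweeteners should have an effect on our endpoints, we might combine the two arms for an additional analysis". That analysis is 20 without sweetener against 40 with.

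No test, threshold, direction or endpoint is given for *effect*. Two meanings can be drawn from the text:

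- **Against control.** This is the comparison that section 10.4.1 has just described, read with the threshold in section 10.4.2: "Differences will be considered to be significant when P < 0.05".
- **Against baseline.** Section 10.4.2 says "Student's paired t-test will be used to test for significant differences between subjects before and after sweetener intake", and section 10.1 frames the expectation the same way: "We expect that glycaemic control is ameliorated in obese, non-diabetic (but insulin resistant) patients compared to baseline".

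Section 10.4.3 states: "No secondary analyses or subgroup analysis is planned".

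**The concern.** Whether the pooled result appears depends on the data that produce it. The two single-arm results share one control arm, so a control mean that is low or high by chance pushes both in the same direction, helps to meet the condition, and then enters the pooled estimate. A pooled effect shown only after such a filter is biased away from zero.

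The gain in precision from pooling matters most when each arm alone is inconclusive. In that case the plan provides no pooled analysis.

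Section 10.2 says that the findings will be used to plan larger studies, so estimation is the main product of this pilot. An estimate that has passed a significance filter is a poor basis for planning.

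**Working it through.** **Inputs from the protocol.** 20 per arm (10.2); drop-outs replaced (10.4.1), so 20 completers per arm; P < 0.05 (10.4.2); pooled comparison 20 + 20 = 40 against 20, which agrees with the stated sizes. The choice of 20 cannot be reproduced, because no SD, CV or power is given.

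**Assumptions.** Normal outcome with SD 1, two-sided tests, baseline to follow-up correlation 0.5, pooled-variance t-tests on follow-up values, the same true effect in both sweetener arms unless stated. About 200,000 simulated trials per scenario.

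**Precision available.** The standard error of a difference is √(1/20 + 1/20) = 0.316 SD for one arm against control and √(1/40 + 1/20) = 0.274 SD for the pooled comparison. The effect detectable with 80% power falls from 0.91 to 0.78 SD.

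**Meaning 1: both arms significant against control, same direction**

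| True effect (SD) | Condition met | Pooled P < 0.05 when met | Mean pooled estimate when met (SD) | Estimate / truth | Pooled power if always run |
|---|---|---|---|---|---|
| 0.4 | 11% | 100% | 0.84 | 0.84/0.4 = 2.1 | 30% |
| 0.6 | 29% | 100% | 0.90 | 0.90/0.6 = 1.5 | 58% |
| 0.8 | 55% | 100% | 0.98 | 0.98/0.8 = 1.2 | 82% |
| 1.0 | 79% | 100% | 1.09 | 1.09/1.0 = 1.1 | 95% |

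At 0.5 SD the condition was met in 37,426 of 200,000 trials (19%) and no pooled test among them failed. The pooled test run always would be significant in 44% of trials, so about 1 − 0.19/0.44 = 57% of significant pooled results would not be produced under the rule. With no true effect the condition is met in about 0.9% of trials.

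**Meaning 2: both paired before-after tests significant, same direction**

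| True effect (SD) | Condition met | Pooled P < 0.05 when met | Mean pooled estimate when met (SD) | Excess over truth |
|---|---|---|---|---|
| 0.3 | 6% | 35% | 0.44 | about 46% |
| 0.5 | 32% | 55% | 0.57 | about 15% |
| 0.65 | 62% | 70% | 0.69 | about 6% |
| 0.8 | 85% | 84% | 0.82 | about 2% |

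With correlation 0.8 and a true effect of 0.5 SD the excess is about 2%, and 45% of the pooled tests are significant. If all three arms drift by 0.5 SD and neither sweetener does anything, the condition is still met in 32% of trials; the pooled test against control is then significant in 5%.

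**Direction not required.** With true effects of +0.9 and −0.9 SD, both arms differ significantly from control in 59% of trials, and the pooled test is significant in about 0%.

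**One active arm.** With 1.0 SD in one arm and 0 in the other, the pooled test has 37% power against 87% for the active arm alone, and the pooled value, (1.0 + 0)/2 = 0.5 SD, describes neither sweetener.

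**The case against.** Several objections are sound.

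- A reader might infer that the pooled test is always significant. That holds only under the first meaning, which the protocol does not state. Under the paired meaning it fails often, and with opposite directions it almost always fails.
- A reader might infer that pooling is forbidden otherwise. The text says only that the arms might be combined, as an additional analysis, and section 10.4.6 lets deviations be reported and justified.
- Large inflation belongs to modest effects. The only effect that the protocol names is in section 10.2, where 20 per arm is expected to "detect large differences in parameters (> 50%) between the treatments groups". With an assumed CV of 0.5 or 0.4, a 50% difference is 0.5/0.5 = 1.0 SD or 0.5/0.4 = 1.25 SD, and the excess under the first meaning is then 9% or 2%. A higher CV would make it larger.
- One could argue that a trial sized on 0.84 SD when the truth is 0.40 SD would have (0.40/0.84)² = 23% of the patients needed. Nothing says that the pooled estimate would be used in this way, and the separate-arm comparisons are planned without any condition.
- False-positive error is not inflated, and this is an exploratory pilot.
- Declining to pool two different substances unless both act is a defensible scientific idea, as the one-active-arm case shows.
- The conflict with section 10.4.3 is weak, because an optional analysis is not clearly a planned secondary one.

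The definition of *effect* could also be left to a statistical analysis plan. The dependence on results could not: section 10.4.1 states it, and the selection remains under either definition. The worry about dissimilar sweeteners is met better by always showing the arms separately, with their difference, than by a significance filter.

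**Conclusion.** The point stands in a limited form. The rule as written makes an optional pooled analysis depend on results and leaves the condition undefined, so the pooled estimate is selectively reported and tends to be too large. The size depends on the meaning of *effect*: about 2.1 times the truth at 0.4 SD, falling to 1.1 times at 1.0 SD, if it means significance against control in the same direction; about 2% to 46% too large for true effects from 0.8 down to 0.3 SD if it means the paired test. Under the first meaning the pooled P value adds no evidence. Under the second, drift alone can trigger the analysis.

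The true effects, normality, two-sidedness and correlation are assumptions and not protocol figures. The separate-arm analyses are unaffected. The change is worth making because the trial is meant to inform later studies and the correction is nearly free.

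**What to change.** Replace the pooling sentence in section 10.4.1 with text along these lines: *As an exploratory analysis, the mean of the two sweetener arms minus control will be estimated on the primary glycaemic endpoint and reported with a 95% confidence interval whatever the single-arm results. It will always be shown beside each arm's comparison with control and the erythritol minus xylitol difference.*

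The protocol names no baseline-adjusted model, and none is needed for this. The estimate can be taken as a contrast with weights ½, ½ and −1 in the one-way ANOVA of section 10.4.2. The glycaemic variable should be named, and section 10.4.3 should mention this contrast so that the two sections agree.

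The cost is a few sentences and one extra contrast, with no added participants or measurements. The downside is that the pooled value describes neither sweetener if the two differ, so it must stay supplementary to the separate-arm results.

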10.4.2 Primary Analysis

Descriptive statistics will be used for demographic variables, such as age, weight, height and BMI. Hormone and glucose profiles will be analyzed by calculating the area under the concentration-time curve (AUC) from baseline values. The parameters will be tested for normality by the Shapiro-Wilk test method. One-way ANOVA will be applied to describe differences between the groups. Student's paired t-test will be used to test for significant differences between subjects before and after sweetener intake. All statistical analysis will be done using the statistical software package, SPSS for Windows, Version 22.0 (SPSS Inc., Chicago, USA). Values will be reported as mean \pm SEM. Differences will be considered to be significant when P < 0.05. Statistics will be done by the principal investigator with support of Prof. [name], biostatistician.

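### A sweetener effect can be declared from within-arm before-after t-tests that cannot exclude drift, while the valid comparison with control is left without baseline adjustment

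*Protocol*

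**What the plan says.** Section 10.1 frames the expected effect against the participants' own starting values: "We expect that glycaemic control is ameliorated in obese, non-diabetic (but insulin resistant) patients compared to baseline".

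Section 10.4.1 describes three uses of the data:
- Before-after: "Data from each participant before and after treatment will be analyzed in the sweetener groups". For the control arm there is a stability check: "The control group will also be examined twice, and the two time-points should yield similar results".
- Between arms: "Post-treatment values of both treatment groups will then be compared to the control group (without treatment)".
- Baseline: "Baseline values of all three groups will be compared, to rule out any baseline differences".

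Section 10.4.2 names the methods: "Student's paired t-test will be used to test for significant differences between subjects before and after sweetener intake" and "One-way ANOVA will be applied to describe differences between the groups". One threshold covers both: "Differences will be considered to be significant when P < 0.05".

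No rule says which comparison decides whether a sweetener works. The change in the control arm is not formally contrasted with the change in the sweetener arms. No covariate is named for the between-arm comparison, although an OGTT is done at both V2 and V3 in all three arms.

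**The concern.** The trial randomises to a concurrent control, and that control is what separates a sweetener effect from whatever else moves OGTT values over seven weeks. A paired test inside a sweetener arm does not use it. Season, familiarity with the test, weekly calls, diary keeping, care around a nutrition clinic before bariatric surgery, or regression to the mean can all shift the values. (Regression to the mean is probably the smaller issue, since section 6.1 sets no glucose threshold for entry.) Because the expectation in 10.1 is set against baseline and the paired test carries a significance threshold, a report could claim a sweetener effect on this test alone. Seeing that control values look similar at both visits does not repair it: a significant change in one arm and none in another is not a test of the difference between them.

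The comparison with control answers the right question, but less precisely than the data allow. With 20 per arm, precision is scarce. Section 10.2 says the findings will be used to plan larger studies, so both a drift-contaminated estimate and an imprecise one carry a cost.

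**Working it through.** **The plan's own figure.** Section 10.2 says 20 per arm will most likely detect differences above 50% between groups, with no SD, coefficient of variation (CV) or power. It can be neither confirmed nor refuted. By the normal approximation, 80% power for a 50% difference needs CV ≤ 0.5 / [(1.960 + 0.842) × √(2/20)] = 0.56.

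**Inputs from the protocol.** 20 per arm (10.2); significance at 0.05 (10.4.2), taken as two-sided because sidedness is not stated.

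**Assumptions.** The protocol gives no drift and no pre-post correlation r. Drift is shown over 0.1 to 0.5 SD of the change, r at 0.5 and 0.7.

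**Step 1: paired test, no sweetener effect, drift shared by all arms.** The test statistic is noncentral t with 19 degrees of freedom and noncentrality drift × √20; the critical value is 2.093. The last column is 1 − (1 − p)², treating the two arms as independent.

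| Drift (SD of change) | Noncentrality | p: one arm significant | At least one of two sweetener arms |
|---|---|---|---|
| 0 | 0 | 5% | 10% |
| 0.1 | 0.447 | 7% | 14% |
| 0.2 | 0.894 | 14% | 25% |
| 0.3 | 1.342 | 25% | 43% |
| 0.5 | 2.236 | 56% | 81% |

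**Step 2: between-arm comparison under the same drift.** A shared drift cancels. In 20,000 simulated trials with drift 0.3 SD and no effect, one-way ANOVA on post-treatment values rejected in 5.1% (r = 0.5). The issue here is precision, not validity.

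**Step 3: precision of one sweetener-versus-control contrast.** The detectable difference at 80% power comes from the noncentral t with 38 degrees of freedom and noncentrality d × √(20/2). ANCOVA multiplies the residual SD by √(1 − r²), which is 0.866 at r = 0.5 and 0.714 at r = 0.7. Losing one degree of freedom to the covariate changes the results by no more than about 0.001 SD.

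| Two-sided alpha | Unadjusted | ANCOVA, r = 0.5 | ANCOVA, r = 0.7 |
|---|---|---|---|
| 0.05 | 0.91 SD | 0.91 × 0.866 = 0.79 SD | 0.91 × 0.714 = 0.65 SD |
| 0.025 (Bonferroni, two contrasts) | 1.01 SD | 0.87 SD | 0.72 SD |

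Power for a true difference of 0.6 SD, like for like:

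| Two-sided alpha | Unadjusted | ANCOVA, r = 0.5 | ANCOVA, r = 0.7 |
|---|---|---|---|
| 0.05 | 46% | 57% | 74% |
| 0.025 | 34% | 45% | 63% |

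In sample-size terms, 20 / (1 − r²) gives 27 per arm at r = 0.5 and 39 at r = 0.7: that many on post-treatment values alone would match 20 with ANCOVA.

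**Step 4: what a baseline test can exclude.** The largest non-significant gap between two arms is t(0.975, 38) × √(2/20) = 2.024 × 0.316 = 0.64 SD. A non-significant result therefore does not rule out a sizeable chance imbalance.

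**The case against.** The strongest reply is that the protocol does plan a controlled comparison. Section 10.4.1 compares both sweetener arms with control, 10.4.2 assigns one-way ANOVA to group differences, and the threshold is not reserved for the paired test. This stands. A reader might infer that the paired test is the only test of a sweetener effect and that the randomised comparison is discarded. The documents do not support that; it would hang on the single verb used for the ANOVA. Nor does drift count as effect everywhere: it does so only in the paired tests. Nor are baseline data wasted: they feed the paired tests and the baseline check, and are absent only from the between-arm contrast. An unadjusted comparison of randomised post-treatment values is unbiased, so its cost is precision.

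A second reply is that the protocol's named non-sweetener causes, replacement of sucrose and a placebo response, do not support the case for ANCOVA. This also stands. Both arise from receiving a sweetener, the untreated control does not share them, and ANCOVA against that control would leave them in the estimate.

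Third, section 10.1 calls the study an exploratory pilot to which hypothesis testing does not apply. That lowers the severity, but 10.4.2 still sets a significance threshold. Fourth, a separate analysis plan could name a covariate. It could, but the protocol itself fixes post-treatment values as the quantity compared. The phrase in 10.4.2 about AUC from baseline values most naturally refers to the time-0 OGTT sample, not to adjustment for V2.

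**Conclusion.** The point holds in this limited form. The plan lets a sweetener effect be declared from a within-arm test whose false-positive rate, under an assumed shared drift of 0.1 to 0.5 SD of the change, runs from 7% to 56% per arm against a nominal 5%. The planned comparison with control is free of that problem but gives up precision: its detectable difference is 0.91 SD where ANCOVA would reach 0.79 or 0.65 SD at two-sided 0.05, and 1.01 SD against 0.87 or 0.72 SD at 0.025. Drift size and correlation are assumptions. With no drift the paired test keeps its 5% level, and with a low correlation the precision gain is small. Because the study is an exploratory pilot and a valid controlled comparison is already planned, this should be fixed; it is not a fatal flaw.

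**What to change.** - In 10.4.2, make the primary analysis one ANCOVA across all three arms for each glycaemic measure: V3 value as outcome, the same participant's V2 value as covariate, arm as factor. Pre-specify two contrasts, xylitol minus control and erythritol minus control, each reported as a difference with a 95% CI. State whether the two contrasts are adjusted for multiplicity, and quote any power figure at the matching alpha.
- In 10.1, state the expectation relative to the control group instead of relative to baseline.
- In 10.4.1 and 10.4.2, report paired changes descriptively in all three arms, without significance tests.
- In 10.4.1, replace the baseline significance tests with a descriptive baseline table.
- Add a sentence that sucrose replacement and placebo response arise only in the sweetener arms and are not removed by baseline adjustment.

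The cost is protocol wording and an amendment. No new data are needed, because V2 and V3 values are already collected in every arm.

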3.2 Primary Objective

Glycaemic control (fasting insulin & glucose & c-peptide after oral glucose challenge)

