4. STUDY OUTCOMES

4.1 Primary Outcome

Glycemic control: Before and after treatment, an oral glucose tolerance test will be carried out. In this trial, we will include more time-points (0-30-60-90-120min. after glucose ingestion) for an accurate assessment of pharmacokinetics (AUC: area under the curve, Cmax, Tmax).

STANDARD ORAL GLUCOSE TOLERANCE TEST: DEFINITIONS

Diabetes: Fasting plasma glucose ≥7.0mmol/l or ≥11.1mmol/l (OGGT: 2-h plasma glucose))

Impaired Glucose Tolerance (IGT): Fasting plasma glucose <7.0mmol/l and ≥7.8 and <11.1mmol/l (OGGT: 2-h plasma glucose)

Impaired Fasting Glucose (IFG): Fasting plasma glucose 6.1 to 6.9mmol/l and <7.8mmol/l (OGGT: 2-h plasma glucose).

Definition and Diagnosis of Diabetes Mellitus and Intermediate Hyperglycaemia: Report of a WHO/IDF consultation. World Health Organization 2006

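### No single OGTT measure is named as primary, within-arm and between-group tests all count at a flat 5% level that conflicts with section 10.1, and pooling of the polyol arms depends on undefined results

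*Protocol*

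**What the plan says.** Section 3.2 gives the primary objective as "Glycaemic control (fasting insulin & glucose & c-peptide after oral glucose challenge". Section 4.1 adds that the sampling times serve an "accurate assessment of pharmacokinetics (AUC: area under the curve, Cmax, Tmax". No analyte or summary is put ahead of the others.

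In section 10.4.2, "Hormone and glucose profiles will be analyzed by calculating the area under the concentration-time curve (AUC) from baseline values". Two kinds of test follow. "One-way ANOVA will be applied to describe differences between the groups", and paired t-tests compare values before and after sweetener intake. The decision rule for all of them is "Differences will be considered to be significant when P < 0.05". Section 10.4.1 also says that post-treatment values of both polyol groups will be compared with control.

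Section 10.1 states the opposite position: "In this exploratory pilot study a hypothesis testing is non-applicable".

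On pooling, section 10.4.1 says: "In case both sweeteners should have an effect on our endpoints, we might combine the two arms for an additional analysis", namely no sweetener (n = 20) against sweetener (n = 40). It does not say what counts as an effect, on which endpoint, or by which test.

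**The concern.** A plan that names no primary measure and applies several tests to each candidate offers many routes to a statement that glycaemic control improved. Each route carries its own 5% error, and nothing in the protocol says which one decides.

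The within-arm tests carry a further problem. A change over seven weeks in an arm whose participants know they receive a sweetener is not a contrast with control. Section 5.2 itself accepts a possible placebo effect and possible substitution of sugar.

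Pooling only after both arms look favourable selects trials in which chance helped, so the pooled estimate is too large on average. Sections 10.1 and 10.2 say that the findings will serve to plan larger studies. A chance finding or an inflated estimate would carry forward into their design.

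**Working it through.** **Inputs from the protocol.** 20 participants per arm and three arms (section 10.2). Three analytes (section 3.2). AUC as the analysed summary (section 10.4.2), with Cmax and Tmax also listed (section 4.1). Two within-arm paired t-tests and one ANOVA per measure, each at 0.05 (section 10.4.2). The protocol states no familywise error rate, SD or power, so there is no figure of its own to reproduce.

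**Assumptions, not in the protocol.** Two-sided tests, normal data, a correlation of 0.6 between a participant's baseline and follow-up values, and equal correlation ρ among measures, varied from 0 to 0.7. The ANOVA is run on post-treatment values.

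**Count of measures.**
- Narrow reading: 3 AUCs × 3 tests = 9 tests.
- Wide reading: 3 analytes × 4 summaries (fasting, AUC, Cmax, Tmax) = 12 measures, and 12 × 3 = 36 tests. The figure 12 is inferred from sections 3.2 and 4.1 and is not printed anywhere.

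**Closed-form reference, independent tests:** 1 − 0.95^k.
- k = 3: 14.3%
- k = 9: 37.0%
- k = 12 (ANOVA alone on 12 measures): 46.0%
- k = 36: 84.2%

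**Simulation under no effect.** Chance of at least one P below 0.05 (20,000 trials per row):

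| Measures | ρ | ANOVA + two paired tests | ANOVA only |
|---|---|---|---|
| 1 | – | 14% | 5% |
| 3 (AUCs) | 0 | 36% | 15% |
| 3 (AUCs) | 0.5 | 32% | 13% |
| 3 (AUCs) | 0.7 | 29% | 11% |
| 12 | 0 | 83% | 45% |
| 12 | 0.5 | 68% | 33% |
| 12 | 0.7 | 55% | 24% |

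Measures taken from one five-point curve overlap, so ρ = 0 is an upper bound. In separate simulations (4,000 trials each), 12 measures at ρ = 0.8 and 0.9 gave 46% and 34%. Measures computed from simulated five-point profiles for three analytes, with assumed means and variances, gave 64–76% for the 12.

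**Pooling and the first false positive.** If the pooled test is run only when both arms are already significant on the same measure, a significant result exists before it is run. It adds 0.0 points.

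**Pooling and the estimate.** 60,000 trials per effect size, the same true effect in both polyol arms, and pooled polyol minus control on post-treatment values:

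| True effect | Trigger: both arms significant on | Pooled test significant, given trigger | Mean pooled estimate, given trigger |
|---|---|---|---|
| 0.5 SD | paired tests | 51% | 0.55 SD |
| 0.5 SD | tests against control | 100% | 0.87 SD |
| 0.3 SD | paired tests | about 30% | 0.41 SD |
| 0.3 SD | tests against control | 100% | 0.81 SD |

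Without a trigger the mean estimate equals the true effect in both cases.

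**The case against.** The best defence is that this is a pilot. Familywise control is not a settled requirement in exploratory work, and a particular adjustment is partly a matter of preference. That stands, and it is why dropping the significance rule is an acceptable remedy. It does not rescue the text as written. Section 10.4.2 declares significance, and the statistical considerations in the local-language summary expect relevant changes to reach statistical significance with at least 20 per group.

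A separate analysis plan could name one measure or adjust for multiplicity. But the protocol does not defer the matter: it fixes the tests and the threshold itself.

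Three stronger readings are tempting, and the documents do not support them.

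- A reader might infer that a false significant primary result is more likely than not. That needs all 12 inferred measures, the within-arm tests counted as primary claims, and an average correlation below about 0.75. Section 10.4.2 names only AUC, which gives 29–36%. ANOVA alone stays below 50% even with 12 measures.
- A reader might infer that the pooled test drives the error rate, or is bound to be significant. Section 10.4.1 makes it optional and additional, and under a significance trigger it adds nothing to the first false positive. It is always significant only if the trigger is each arm against control, which the protocol does not say.
- A reader might take "No secondary analyses or subgroup analysis is planned" in section 10.4.3 to mean that microbiome and metabolomic features will be screened singly at an uncorrected 5%. No section says so. The sentence may only mean that nothing beyond section 10.4.2 is planned, and the handling of such data is commonly left to an analysis plan.

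**Conclusion.** The point holds in three parts.

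1. No single OGTT measure is primary, and within-arm tests count equally with the between-group test. The chance of a false significant result is about 14% even for one measure, 29–36% for the three AUCs, and 55–83% for 12 measures at correlations from 0.7 down to 0. The last range rests on an inferred count.
2. Sections 10.1 and 10.4.2 contradict each other on whether anything is being tested.
3. The pooling trigger is undefined and depends on the results. The upward bias for a true 0.5 SD ranges from slight (0.55 SD) to large (0.87 SD), according to a choice that the protocol leaves open.

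The figures depend on the stated assumptions about correlation and normality. The direction does not. The exploratory label softens the consequence but does not remove it, because the significance rule is written into the primary analysis.

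**What to change.** - Name one primary measure in sections 3.2, 4.1 and 10.4.2, for example plasma glucose AUC 0–120 min at the follow-up metabolic visit (V3). State whether it is total or incremental.
- Base the primary conclusion on xylitol against control and erythritol against control, both from one baseline-adjusted model, and not on within-arm paired tests.
- Either control the two contrasts (Dunnett or Holm) or remove the 5% significance rule so that section 10.4.2 agrees with section 10.1. Reconcile the two sections in either case.
- Report all other OGTT measures and the within-arm changes as exploratory estimates with 95% confidence intervals.
- Report the pooled contrast (mean of the two polyols minus control) from the same model whatever the single-arm results, or delete it.

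**Cost.** Protocol wording only. With 20 per arm and 80% power, the detectable difference for a two-sample t-test is 0.91 SD at 0.05 and 1.01 SD at 0.025. The ratio is 1.01 / 0.91 ≈ 1.11, so Bonferroni costs about 11% and Dunnett less. Baseline adjustment works the other way: at an assumed correlation of 0.6 it multiplies the residual SD by √(1 − 0.36) = 0.8, which brings 1.01 SD down to about 0.81 SD. If the significance rule is dropped instead, there is no cost in detectable effect, but the report can no longer call any result significant.
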